7.7. Lost to Follow-up

The following actions will be taken if a participant fails to return to the clinic for a required study visit:

- The site must attempt to contact the participant and reschedule the missed visit as soon as possible and counsel the participant on the importance of maintaining the assigned visit schedule.
- Before a participant is deemed lost to follow-up, study center personnel must make every effort to regain contact with the participant (ie, where possible, 3 telephone calls and, if necessary, a certified letter sent to the participant's last known mailing address or local equivalent methods). These contact attempts will be documented in the participant's source document.
- If the participant continues to be unreachable, study center personnel or designee will attempt to determine the vital status of the participant within legal and ethical boundaries for all randomized participants, including those who did not receive study drug. Public sources may be searched for vital status information. If vital status is determined to be "deceased," this will be documented and the participant will not be

considered lost to follow-up. Sponsor personnel will not be involved in any attempts to collect vital status.

Should the participant continue to be unreachable and the vital status is unknown, or the participant is determined to be living, he/she will be considered lost to follow-up from the study.

7.8. Replacement of Randomized Participants

If participants prematurely discontinue or are considered lost to follow-up, additional participants may be recruited and enrolled at the discretion of the sponsor.

8. STUDY DRUG AND CONCOMITANT MEDICATION ADMINISTRATION

8.1. Study Drug Regimen

All eligible participants will be randomized to either CY6463 (15 mg QD) or matching placebo QD; see [Table 2](#). Study drug may be taken with or without food. Participants will be instructed to take their daily study drug dose each morning at a consistent time (preferably ± 1 hour) throughout the Treatment period. Participants are to record the date and time of each at-home dose administration in their study diary (see Section [9.9](#)).

Exception/Note: For all scheduled visits that occur on a dosing day, participants will take their dose during the visit to allow for appropriate timing of pre- and post-dose assessments. Attempts should be made to schedule these visits such that dosing can occur at the participant's approximate daily dosing time. In conjunction with these visits, participants will fast for ≥ 4 hours before clinical laboratory samples are collected.

Table 2: Study Drug Identification and Dosing Regimen

	Study Drug	
Product name	CY6463	Placebo to match the CY6463 tablet
Dosage form & description	round, white to off-white solid tablet	round, white to off-white solid tablet
Unit dose strength	5-mg tablet	N/A
Regimen*	15 mg (3 \times 5-mg tablet) taken QD	3 \times PTM tablets taken QD
Route of administration	oral	oral
Sourcing	Provided centrally to the study center pharmacy by the sponsor/designee	
Packaging & labeling	Supplied in white, induction-sealed 60-cc high-density polyethylene bottles that are fitted with a polypropylene child-resistant cap. Each bottle contains a count of 35 tablets and a 3-g silica gel desiccant pack and is labeled as required per country requirement.	

N/A=not applicable; PTM=placebo to match; QD=once daily; study drug=CY6463 or matching placebo

* Regimen to be assigned centrally, via randomization.

Study drug supply and dosing compliance assessment details are provided in Section [8.3](#).

8.2. Dose Modification in Individual Participants

For a participant who does not tolerate the 15-mg QD dose (ie, three 5-mg tablets) as evidenced by an associated AE, the participant's dose may be de-escalated to 10-mg QD dose (ie, two 5-mg tablets).

- The decision to de-escalate study drug will be made on a per-participant basis jointly by the investigator and the CRO-based medical monitor, in consultation with the sponsor's medical monitor as needed; the modification will be recorded in the source documents and eCRF.
- Initiation of the 10-mg QD dose should occur only after the AE(s) prompting the dose reduction has/have either resolved or improved sufficiently to be considered mild in severity or, if the AE is a worsening of a pre-existing condition, has returned to baseline status.

If the 10-mg QD dose is also not tolerated, the participant will be discontinued from study drug for the remainder of the Treatment period due to the AE. See Section [7.6](#) for additional study drug discontinuation criteria and procedures.

8.3. Study Drug Supply and Dosing Compliance

The appropriate amount of study drug will be dispensed to randomized participants on Day 1. Drug will be resupplied as needed.

When participants are dosed at the study center, they will receive study drug under medical supervision, directly from the investigator or designee who will examine the participant's mouth to ensure that study drug was ingested. The study drug dose and the participant's identification will be confirmed at the time of dosing by a member of the study site staff other than the person administering the study drug. The date and time of each dose administered in the clinic will be recorded in the source documents.

Participants and/or their caregivers/study partners, as applicable, will be asked to record the date and time of each at-home study drug administration in their daily study diary (Section [9.9](#)). They will be asked to bring their diary to each scheduled visit. The diaries will be checked for dosing compliance; as applicable, participants will be reminded of the need for daily compliance with dosing.

During the Treatment period, participants will also be asked to bring their study drug supply in the original bottles to each scheduled visit. Study drug dosing compliance will be based on tablet counts conducted during the Treatment period and will be documented in the source documents and relevant eCRF. Deviation(s) from the assigned regimen will be recorded, including dates for dosing delays and/or dose reductions.

8.4. Treatment and Tracking of Overdose

For this study, any reported daily dose of study drug >15 mg QD will be considered an overdose whether or not associated with an AE(s).

In the event of an overdose, the investigator/treating physician should:

- Immediately contact the CRO-based medical monitor
- In consultation with the CRO-based medical monitor, evaluate the participant to determine whether study drug should be interrupted, whether the subsequent dose should be reduced, and/or if plasma PK sample should be obtained
- Closely monitor the participant for any AE(s)
- Document the quantity of the excess dose as well as the duration of the overdose

8.5. Continued Access to Study Drug after the End of the Study

Continued access to study drug after cessation of an individual's study participation is not planned.

8.6. Study Drug Preparation, Handling, Storage, and Accountability

Study drug must be stored in a secure, monitored (manual or automated) area in accordance with the labeled storage conditions and with access limited to the investigator and authorized study center staff.

Study drug should be kept at room temperature (ie, 50°–86°F) at all times. Participants will be advised to report any excursion outside of this temperature range to study center staff. Study drug bottles must be kept tightly closed.

8.6.1. Accountability

The investigator/designee must confirm that appropriate temperature conditions have been maintained during transit for all study drug received and that any discrepancies are reported and resolved before use of the study drug.

Only participants who are eligible per this protocol for study drug administration may receive study drug. Only authorized study center staff may supply study drug to the participants.

The investigator, institution, or the head of the medical institution (where applicable) is responsible for study drug accountability, reconciliation, and record maintenance (ie, receipt, reconciliation, and final disposition records). A copy of the final drug accountability log will be provided to the sponsor or designee.

8.6.2. Disposal

Refer to the study's pharmacy manual for study drug disposal instructions. No study drug is to be destroyed without prior written permission of the sponsor.

8.7. Concomitant Medications and Therapies

Any medication or vaccine (including over-the-counter or prescription medicines, recreational drugs, vitamins, and/or herbal supplements, or other specific categories of interest) that the

participant is receiving at the time of enrollment or receives during the study must be recorded along with:

- Reason for use
- Dates of administration including start and end dates
- Dosage information including dose and frequency

Note: Prior therapies, medications, vaccinations, surgeries, etc. (ie, before initiation of study drug) must be differentiated from concomitant therapies (ie, those after initiation of study drug) to facilitate understanding of any AEs that occur after the start of study drug.

See Section [8.7.1](#) for information on medications that are prohibited in this study. In addition, participants will not initiate the use of additional medication (including nonprescription “over-the-counter” preparations) for treatment of AD during the study other than the study drug.

The CRO-based medical monitor should be contacted if there are any questions regarding concomitant or prior therapy.

8.7.1. Prohibited Medications

Comprehensive drug-drug interaction studies with CY6463 have not been conducted in humans. See [Appendix 3](#) for a complete list of medications that are prohibited. Participants and/or their caregivers/study partners should be reminded of the restrictions on food, beverages, supplements, and other substances as noted in Section [7.5](#).

The decision and need to switch medications and/or dose-reduce concomitant medications prior to or during study drug exposure will be made by the investigator in consultation with the study center pharmacist (if available) or the CRO-based medical monitor to assess the risk/benefit of administering the concomitant medication.

9. STUDY ASSESSMENTS AND PROCEDURES

Study assessments will be conducted according to the timing and sequence indicated in the [Schedule of Events](#). Details regarding those procedures are provided below and in the study manuals (eg, laboratory, pharmacy, imaging).

During any unscheduled visit, safety assessments will be conducted per investigator discretion; results will be documented in the source document and the appropriate eCRF.

9.1. Informed Consent

Before a potential study participant undergoes any study-specific evaluations or procedures, the participant (and/or participant's LAR/guardian, if applicable) must provide written, informed consent. See [Appendix 1](#) for more information.

9.2. MMSE

The Mini-Mental State Examination (MMSE) consists of 11 questions that together test 5 areas of cognitive function: orientation, registration, attention, and calculation, recall, and language.

The maximum score is 30. A score of 23 or lower is indicative of cognitive impairment, and 17 or lower indicates severe impairment.

9.3. Demography, Medical History, and Baseline Medications

At the Screening visit, demographic characteristics (eg, age, sex, race/ethnicity, apolipoprotein E4 [ApoE4] status if known, and highest level of education completed) will be recorded along with a complete medical history that will include the participant's diagnosis of AD, evidence of vascular pathology, smoking history, prior and current medications (see Section 8.7), surgeries, and any additional relevant medical history.

9.4. Physical Examination

At Screening, a complete physical examination will be performed by the investigator and documented on the appropriate eCRF. All other examinations may be symptom directed at the investigator's discretion.

A complete physical examination should include examination and assessment of the following:

General appearance	Lymph nodes	Nervous system
Cardiovascular system	Head, eyes, ears, nose, and throat	Skin
Respiratory system	Neck	Mental status
Abdomen/liver/spleen	Musculoskeletal system	

Breast, genitourinary, and rectal examinations are optional and may be performed at the discretion of the investigator.

Height (cm) will be measured only at Screening. Weight (kg) will be recorded throughout the study per [Table 1](#). BMI will be calculated and recorded at Screening.

9.5. Electrocardiograms (ECGs)

All ECGs will be obtained using an ECG machine that automatically calculates the heart rate and measures PR, QRS, QT, and QTc intervals. The ECG should be obtained after the participant has rested supine for ≥ 5 minutes.

If a QTc result (corrected using Fridericia's formula) is outside of the normal range (>450 ms), the ECG should be repeated twice and the average of the 3 results calculated.

All ECGs will be evaluated by an investigator or qualified designee for the presence of abnormalities. Results will be reported as "normal," "abnormal clinically significant," or "abnormal not clinically significant." Abnormalities of clinical significance will be recorded as an AE.

If a confirmed clinically significant abnormal result is obtained, the study center should follow standard institutional procedure until the result resolves to baseline. If concerns remain, escalate the issue to the sponsor's medical monitor.

9.6. Vital Signs

Vital signs will be measured before blood collection(s) and will include oral temperature (°C), respiratory rate, peripheral oxygen saturation, and seated-to-standing BP and pulse rate. All measures should be preceded by ≥ 5 minutes of rest for the participant in a quiet setting without distractions (eg, television, cell phones).

Oxygen saturation measurements should be taken by pulse oximeter on room air.

BP and pulse will be measured using a completely automated device. The same device make/model should be used for an individual participant throughout the study, if possible. Manual techniques will be used only if an automated device is not available.

- *Supine/semi-recumbent BP measurements:* 3 consecutive BP readings will be recorded in the source documents at intervals of approximately 1 minute. The average of the 3 BP readings will be recorded in the eCRF.
- *Orthostatic BP and pulse measurements:* After the supine/semi-recumbent measurements are collected, the participant will assume a sitting position for 1 to 3 minutes, and finally assume a standing position for 2 (± 1) minutes before the standing BP and pulse values are measured (single measure); these values will be recorded in the source document.
- The supine/semi-recumbent average and the standing values will be used to calculate and record orthostatic BP and pulse in the eCRF.

9.7. Laboratory Assessments

9.7.1. Genetics

Participants who do **not** have ApoE4 genetic status recorded in their medical records will be tested for ApoE4 status and for ABCA7 (adenosine 5-triphosphate [ATP]-binding cassette sub-family A, member 7) status (if not already in their medical record), and potentially for additional genetic polymorphisms associated with endothelial dysfunction at Screening. Collection instructions are provided in the study's laboratory manual.

9.7.2. Safety Laboratory Assessments

Tests detailed in [Table 3](#) will be performed per [Table 1](#) and sent to the central laboratory for analysis. See the study's laboratory manual for collection and processing details.

Except at Screening, participants will fast for ≥ 4 hours prior to safety laboratory sample collections.

On **Day 1** prior to randomization, clinical safety laboratory results (clinical chemistry, coagulation, and hematology) from the Day 1 predose sample (see [Table 1](#) footnote b) must be reviewed for clinical significance to confirm eligibility and suitability for this study; local laboratory values may be used for this purpose provided that a separate set of the Day 1 samples is sent to the Central laboratory for processing and for recording in the eCRF. Laboratory parameter requirements for study eligibility are detailed in [Section 7.1](#) and [Section 7.2](#).

Throughout the study, the investigator is responsible for reviewing each laboratory report and for determining the clinical significance of any results that fall outside of the laboratory normal ranges; this review must be documented and filed with the source documents. Additional tests may be performed at any time during the study per investigator discretion or as required by local regulations. Laboratory assessments may also be repeated if an error is suspected.

An abnormal laboratory value not already part of a diagnosis and that requires a change in the study drug or is considered clinically significant by the investigator is to be recorded as an AE.

All laboratory values considered abnormal and clinically significant during study participation, including the Follow-up visit, should be repeated until the values return to normal or baseline or are no longer considered clinically significant by the investigator or the CRO-based medical monitor.

Table 3: Protocol-Required Laboratory Assessments

Assessment	Parameter		
Hematology	Hematocrit	RBC indices: --Mean corpuscular hemoglobin (MCH)	WBC count w/differential: --Basophils --Monocytes
	Hemoglobin	--Mean corpuscular volume (MCV)	--Eosinophils --Neutrophils
	Platelet count	--%Reticulocytes	--Lymphocytes
	RBC count		
Clinical chemistry (serum)	Albumin	BUN	GGT
	Alkaline phosphatase	Calcium	Glucose (fasting)
	ALT/SGPT	Creatinine	Potassium
	AST/SGOT	Creatine kinase	Protein (total)
	Bilirubin (total, direct)	Cystatin C	Sodium
Coagulation	aPTT	INR	Prothrombin time
Lipids	Total cholesterol	HDL-c	LDL-c
			Triglycerides

Note: Events of ALT $\geq 3 \times$ upper limit of normal (ULN) and bilirubin $\geq 2 \times$ ULN ($>35\%$ direct bilirubin) or ALT $\geq 3 \times$ ULN and INR > 1.5 , which may indicate severe liver injury (possible Hy's Law), will be reported as an SAE.

ALT=alanine aminotransferase; aPTT=activated partial thromboplastin time; AST=aspartate aminotransferase; BUN=blood urea nitrogen; GGT=gamma glutamyl transferase; HDL-c=high-density lipoprotein cholesterol; INR=international normalized ratio; LDL-c=low-density lipoprotein cholesterol; RBC=red blood cell; SGOT=serum glutamic-oxaloacetic transaminase; SGPT=serum glutamic-pyruvic transaminase; WBC=white blood cell

9.7.3. PK and Biomarker Evaluations (Plasma and CSF)

Samples will be collected per the [Schedule of Events](#) and the study laboratory manual. The actual date and time (24-h clock time) of each sample collection will be recorded in the source documents and eCRF. Specific instructions for the collection and handling of biological samples are provided in the study's laboratory manual.

Samples collected for biomarker analysis will be used to further understand the ADv disease process, pathways associated with the disease state, and/or the mechanism of action of CY6463 and its PD effect.

9.7.3.1. Plasma Sampling

Sparse whole-blood samples will be collected for measurement of plasma concentrations of CY6463 using a validated liquid chromatography-tandem mass spectrometry bioanalytical method. Blood samples will also be collected to evaluate changes in concentrations of select disease and PD biomarkers.

9.7.3.2. CSF Sampling

CSF samples will be collected for measurement of CY6463 concentrations and for changes in the concentrations of select disease and PD biomarkers.

9.8. Suicidal Risk Monitoring (C-SSRS)

CY6463 is considered to be a CNS-active investigational drug. Although CY6463 and other similar drugs in this class have not been associated with an increased risk of suicidal thinking or behavior, the sponsor considers it important to monitor for such ideation or behavior before and during this clinical study. Therefore, participants should be appropriately monitored and closely observed for suicidal ideation and behavior or any other unusual change in behavior. The C-SSRS (13) will be administered per the [Schedule of Events](#) by an individual with appropriate clinical training who has taken the specific rater training for the scale, which will be provided by an agent of the sponsor prior to study start. If at any post-Screening visit there are “YES” answers on Items 4, 5 or on any behavioral question of the C-SSRS, an immediate risk assessment should be conducted with the CRO-based medical monitor to determine whether it is safe for the participant to continue in the study.

9.9. Participant Diary for Recording Daily Dosing, Concomitant Medications, and Changes in Health Status

At the Screening visit, each participant will be issued a study diary in which they (or their LAR/guardian or caregiver/study partner, as applicable) will be asked to record on a daily basis the name of any new and/or changes in concomitant medication(s) they take, along with the date, time, and dose strength of that medication(s), and any changes in health status that they experience (including the dates, times, and brief descriptions). They will be asked to continue entering this information each day throughout the study until the Follow-up visit. The diaries are intended to serve as reminders to the participant and caregiver/study partner and will constitute official source documents. During the Treatment period, participants will be instructed to also record the date and time of each study drug dose taken at home.

Participants will be asked to bring their diary to each scheduled visit. Study staff will monitor the diaries during the visit, record any relevant data in the eCRF, and will retain the diaries as part of the participants' source files. A new diary will be issued at each visit, with the final diary collected at the Follow-up visit.

9.10. Adverse Events, SAEs, and Other Safety Reporting

The definitions of AEs, adverse events of special interest (AESIs), and SAEs can be found in [Appendix 2](#).

Immediate safety concerns should be discussed with the study's designated CRO-based medical monitor upon occurrence or awareness. Changes in the participant's health status since the previous visit or previous study drug administration must be checked, including laboratory results, as applicable.

9.10.1. Time Period, Frequency, and Reporting Information

AEs, AESIs, and SAEs will be recorded on the AE eCRF starting from the signing of the ICF until the Follow-up visit after the final study drug dose.

- SAEs will be reported within 24 hours of the investigator's first awareness of the event
- Nonserious AESIs will be reported within 5 business days of the investigator's first awareness of the event

9.10.1.1. Follow-up of AEs, AESIs, and SAEs

After the initial AE/SAE report, the investigator is required to proactively follow each participant at subsequent visits/contacts. All SAEs and AESIs will be followed until resolution, stabilization, the event is otherwise explained, or the participant is lost to follow-up (see Section 7.7). The investigator will submit any updated SAE information within 24 hours of it becoming available, using the AE eCRF.

9.10.1.2. Post-Study Events

Investigators are not obligated to actively seek information on AEs or SAEs after conclusion of an individual's study participation. However, if the investigator learns of any SAE, including a death, at any time after a participant has been discharged from the study, and considers the event to be reasonably related to the study drug or study participation, he/she must promptly notify the sponsor.

9.10.2. Method of Detecting AEs and SAEs

AEs will be reported by the participant (or, when appropriate, by the participant's LAR, caregiver, study partner) spontaneously and/or in response to open-ended questioning from the study personnel or revealed by observation. Open-ended and nonleading verbal questioning of the participant will be the preferred method to inquire about AE occurrences. Care will be taken not to introduce bias when detecting events.

See [Appendix 2](#) for details regarding the recording, evaluation, and causality assessment of AEs, AESIs, and SAEs.

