7.1. Inclusion Criteria

Each participant must meet each of the following criteria to be eligible for entering this study.

1. Provides written informed consent prior to the performance of any protocol-specified procedure or, if unable to provide informed consent due to cognitive status, provides assent to participate, with a legally authorized representative (LAR) providing written informed consent on behalf of the participant.

Note:

- If the participant requires a caregiver, a stable caregiver/study partner must also agree to participate as a designated caregiver in the study by agreeing, for example, to

accompany the participant to study visits, manage at-home study drug dosing compliance, and assist with diary completion. See [Appendix 1](#).

- Procedures conducted as part of the participant's routine clinical management (eg, blood count) and obtained before signing of the ICF may be used for screening purposes where noted, provided that the procedures meet the protocol-specified criteria and were performed within the timeframe defined in the [Schedule of Events](#) and/or in the respective eligibility criteria.
- 2. 60 years of age or older on the day of consent
- 3. Meets core clinical criteria for probable AD dementia according to the 2011 National Institute on Aging–Alzheimer's Associated guidelines [\(8\)](#); see [Appendix 4](#). Can be based on medical history.
- 4. Mini-Mental State Examination (MMSE) score of 20 to 26 (inclusive)
- 5. Confirmation of AD pathophysiology either by a prior positive amyloid positron-emission tomography scan or a prior CSF sample (evidence of A β /tau deposition). If AD pathophysiology status is unknown, an aliquot from the screening CSF sample collected for the baseline biomarker assessment can be used to determine AD pathophysiology.
- 6. Presence of ≥ 2 of the following cardiovascular risk factors:
 - a. Hypertension confirmed either by: diagnosis in medical history, use of ≥ 1 ongoing medication to treat hypertension, or consistent (as determined by the investigator) history of systolic and/or diastolic BP values >130 and >80 mmHg, respectively
 - b. Type 2 diabetes or prediabetes confirmed either by: diagnosis in medical history, use of ≥ 1 ongoing medication to treat diabetes, or consistent (as determined by the investigator) history of clinical laboratory values of A1c $\geq 5.7\%$ and/or fasting plasma glucose ≥ 100 mg/dL

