10.4.2. Primary Endpoint(s)

Corresponding with the primary objective of evaluating the safety and tolerability of CY6463, TEAE incidence (number and percentage of participants with TEAEs) will be reported for each

treatment group for the Safety population. A TEAE is defined as an AE that started on or after the administration of randomized study drug through the last day of the Follow-up period.

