APPENDIX 4. NATIONAL INSTITUTE ON AGING / ALZHEIMER'S ASSOCIATION CRITERIA FOR AD DEMENTIA

Source:

All-Cause Dementia: Core Clinical Criteria

The diagnosis of dementia is intended to encompass the spectrum of severity, ranging from the mildest to the most severe stages of dementia. The methodology for staging of dementia severity was beyond the charge of the workgroup. Dementia is diagnosed when there are cognitive or behavioral (neuropsychiatric) symptoms that:

1. Interfere with the ability to function at work or at usual activities; and
2. Represent a decline from previous levels of functioning and performing; and
3. Are not explained by delirium or major psychiatric disorder;
4. Cognitive impairment is detected and diagnosed through a combination of (1) history-taking from the patient and a knowledgeable informant and (2) an objective cognitive assessment, either a "bedside" mental status examination or neuropsychological testing. Neuropsychological testing should be performed when the routine history and bedside mental status examination cannot provide a confident diagnosis.
5. The cognitive or behavioral impairment involves a minimum of 2 of the following domains:
 - a. Impaired ability to acquire and remember new information—symptoms include: repetitive questions or conversations, misplacing personal belongings, forgetting events or appointments, getting lost on a familiar route.
 - b. Impaired reasoning and handling of complex tasks, poor judgment—symptoms include: poor understanding of safety risks, inability to manage finances, poor decision-making ability, inability to plan complex or sequential activities.
 - c. Impaired visuospatial abilities—symptoms include: inability to recognize faces or common objects or to find objects in direct view despite good acuity, inability to operate simple implements, or orient clothing to the body.
 - d. Impaired language functions (speaking, reading, writing)—symptoms include: difficulty thinking of common words while speaking, hesitations; speech, spelling, and writing errors.

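### AE detection for the primary endpoint relies mainly on questioning participants with mild AD dementia; an enrolled caregiver or study partner should be asked routinely, not only at the site's discretion

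*Combined protocol and SAP*

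**What the plan says.** Section 9.10.2 names the participant as the default AE reporter. Others report "or, when appropriate, by the participant's LAR, caregiver, study partner", either spontaneously or when asked, and events may also come to light by observation. It then adds: "Open-ended and nonleading verbal questioning of the participant will be the preferred method to inquire about AE occurrences". No section says when partner input is appropriate or requires that a partner be asked about AEs.

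Inclusion 3 (Section 7.1) applies to everyone: "Meets core clinical criteria for probable AD dementia". Inclusion 4 sets MMSE at 20 to 26. A partner is not mandatory: "If the participant requires a caregiver, a stable caregiver/study partner must also agree to participate". That person's example tasks are coming to visits, managing home dosing and helping with the diary; reporting AEs is not among them. For the diagnosis itself, Appendix 4 uses "history-taking from the patient and a knowledgeable informant".

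Section 10.4.2 defines the primary analysis: "TEAE incidence (number and percentage of participants with TEAEs) will be reported for each" treatment group. No hypothesis test is planned for it (Section 10.1).

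**The concern.** Appendix 4 lists impaired ability to take in and remember new information first among the affected domains, and calls the amnestic presentation the most common. The main source for the primary endpoint is therefore the recall of people whose recall is likely to be impaired. A second observer is used at the discretion of each site, so practice may also differ between sites.

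The events most exposed are short-lived ones between visits. The AESIs in Appendix 2 include dizziness, syncope, symptomatic hypotension and changes such as euphoria. A participant may forget or not recognise these, while a companion may notice them. AE reports also feed the study stopping rules (Section 6.5) and the decisions on dose modification (Section 8.2), so the consequence is wider than one descriptive table.

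**Working it through.** The plan states no TEAE rate, detection rate or power, so there is no figure to reproduce. The calculations below are illustrations.

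**Inputs from the protocol.** About 30 participants randomized 1:1 (Sections 6.2 and 6.3.1), so 30 / 2 = 15 per arm. Visits on Days 1, 15, 29, 58, 87 and 101, with windows of ±4 days from Day 29 on (Table 1).

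**Assumptions.** Detection sensitivity s of 60% to 90%; a true AE rate of 10%; Poisson AE counts per participant in step 3.

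**Step 1: recall intervals.** 15 − 1 = 14, 29 − 15 = 14, 58 − 29 = 29, 87 − 58 = 29 and 101 − 87 = 14 days. With windows, a 29-day interval can reach 29 + 4 + 4 = 37 days.

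**Step 2: seeing at least one case of one event type.** P = 1 − (1 − 0.10s)^15.

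| s | Calculation | P |
|---|---|---|
| 1.0 | 1 − 0.90^15 | 79.4% |
| 0.9 | 1 − 0.91^15 | 75.7% |
| 0.7 | 1 − 0.93^15 | 66.3% |
| 0.6 | 1 − 0.94^15 | 60.5% |

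**Step 3: the arm difference.** For a single event type occurring at most once per participant, with the same s in both arms, the observed risk difference is s times the true one. A true 20-point difference would appear as 0.6 × 20 = 12 to 0.9 × 20 = 18 points, and the risk ratio would not change.

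The primary endpoint is different. A participant with several AEs still counts if one of them is missed. With mean AE counts m0 (placebo) and m1 (CY6463), observed incidence in an arm is 1 − exp(−s·m), and the difference is exp(−s·m0) − exp(−s·m1). In percentage points:

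| Mean AEs, placebo vs CY6463 | s = 1 | s = 0.9 | s = 0.7 | s = 0.6 |
|---|---|---|---|---|
| 0.5 vs 1 | 23.9 | 23.1 | 20.8 | 19.2 |
| 1 vs 2 | 23.3 | 24.1 | 25.0 | 24.8 |
| 2 vs 4 | 11.7 | 13.8 | 18.6 | 21.0 |

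Incidence falls in both arms in every row. For 2 vs 4 it goes from 86.5% vs 98.2% at s = 1 to 75.3% vs 93.9% at s = 0.7. The difference shrinks in the first row, is roughly flat in the second and grows in the third.

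**The case against.** The protocol has several safeguards.

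- Section 9.9 asks for a daily diary of changes in health status. A caregiver may complete it, and staff check it at each visit.
- Section 9.10 requires changes in health since the last visit to be checked.
- Section 9.10.2 already allows partner reports and observed events.
- Table 1 schedules orthostatic vital signs, laboratory tests, C-SSRS and symptom-directed examination at every treatment visit, and ECGs through Day 87.
- The population is mild: MMSE scores of 24 to 26 lie above the impairment cut of 23 in Section 9.2, and Exclusion 1 removes severe cognitive impairment that may affect adherence or assessments. A participant without a partner should be one who does not require a caregiver.
- The sentence on open-ended questioning can be read as being about style rather than about whom to ask.

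Most of this stands, and it makes the risk smaller. It does not close the gap. A participant without a partner keeps the diary alone. The health-status check does not say whom to ask. Scheduled tests can miss a transient episode. On either reading of the sentence, partner input stays conditional and undefined.

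A reader might go further and infer that TEAEs are in fact under-counted, or that missed events shrink the CY6463–placebo difference in proportion. The documents support neither. They contain no detection rate, so under-counting is a risk and not a finding. Proportional shrinkage applies to the risk difference for a single event type. For any TEAE, step 3 shows that the difference can move either way. Both blinded arms use the same detection method, and no test of the primary endpoint is planned.

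**Conclusion.** The point holds as a risk of incomplete ascertainment that is cheap to reduce. The plan leaves it to site discretion whether an enrolled observer is asked, in a trial where the participants' memory is likely to be impaired and the primary endpoint depends largely on what is reported. If events are missed, observed incidence can only be too low.

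The size is unknown. Under assumed sensitivities of 60% to 90%, the chance of seeing a 10% AE at least once in an arm of 15 falls from 79% to between 60% and 76%. This measures the distance from perfect detection. The improvement from routine partner questioning would be some part of it, and the documents give no basis for saying how much. No conclusion is drawn about the arm difference in any TEAE, and no sample-size or power figure changes, because none is stated.

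**What to change.** In Section 9.10.2, replace the discretionary condition with a rule. At every scheduled visit, the same open-ended, nonleading questions are put to the participant and, where one is already taking part in the study, to the LAR, caregiver or study partner, in person or by phone, identically in both arms. Add an eCRF field for the source of each AE, so that the partner's contribution can be described.

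Do not make a partner an entry requirement, since that would restrict enrolment. Do not contact diagnostic informants who have no study role. Inclusion 3 may rest on medical history, so no current informant may exist, and approaching one would raise consent and privacy questions.

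The cost is a wording change, a few minutes per visit, one eCRF field and slightly more AE entries. No extra staff are needed.
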